IUD	Intrauterine device
IUS	Intrauterine system
LDH	Lactate dehydrogenase
LDL	Low density lipoprotein
LMWH	Low molecular weight heparin
MedDRA	Medical dictionary of regulatory activities
NSAID	Nonsteroidal anti-inflammatory drug
OTC	Over the Counter
PRN	Pro re nata – As Needed
RRT	Renal replacement therapy
SAE	Serious adverse event

1.0 LIST OF ABBREVIATIONS

2.0 PHASE 2 PROTOCOL SUMMARY

Study Number:	V0211901
Title:	Randomized, Placebo-Controlled, Phase 2 Study of VERU-111 for the Treatment of Severe Acute Respiratory Syndrome Coronavirus 2 (SARS- CoV-2) in Patients at High Risk for Acute Respiratory Distress Syndrome (ARDS)
Primary Objectives:	To demonstrate the efficacy of VERU-111 in the treatment of SARS-Cov- 2 Infection by assessing its effect on the proportion of subjects that are alive without respiratory failure at Day 29. Respiratory failure is defined as endotracheal intubation and mechanical ventilation, extracorporeal membrane oxygenation, high-flow nasal cannula oxygen delivery, noninvasive positive pressure ventilation, clinical diagnosis of respiratory failure with initiation of none of these measures only when clinical decision making is driven solely by resource limitation.

Secondary	The second	lary objectives/endpoir	ts on this study are:	
Objectives:	1 11/1		1	1. 1
	I. WE	10 Ordinal Scale for C	linical Improvement (8-point	cordinal
	sca	Ie) at Day 15, Day 22, 1 Patient State	and Day 29	Score
		1 unem Stute	Descriptor	Score
		Uninfected	No clinical or virological evidence of infection	0
		Ambulatory	No limitation of activities	1
			Limitation of activities	2
		Hospitalized, Mild disease	Hospitalized, no oxygen therapy	3
			Oxygen by mask or nasal prongs	4
		Hospitalized, Severe disease	Non-invasive ventilation or high- flow oxygen	5
			Intubation and mechanical ventilation	6
			Ventilation + additional organ support – pressors, RRT, ECMO	7
		Death	Death	8
	 Prossati Day Per Day Per Day All Pro 15, Pro Day Pro Day Pro Day 10. Day 11. Pro and 12. Ass bas 	portion of subjects with aration through Day 15 ys on mechanical ventil centage of subjects disc y 22) -cause mortality at Day portion of patients aliv and Day 22 portion of patients aliv y 22, and Day 29 portion of patients aliv y 22, and Day 29 ys in ICU ys in hospital portion of subjects on the l Day 29 sess the pharmacokinet sess the effect of VERU eline)	h normalization of fever and , Day 22, and Day 29 lation charged from hospital by Day 7 15, Day 22, and Day 29 e and free of respiratory failu e and discharged from the IC e and discharged from hospit mechanical ventilation at Day ics of VERU-111 on Day 15 J-111 on C-reactive protein (oxygen y 15 (and ure at Day CU at Day 15, cal at Day 15, y 15, Day 22, change from

CONFIDENTIAL

Safety Objective:	To assess the safety and tolerability of VERU-111
Design:	This study is a multicenter, randomized, placebo-control, efficacy and safety study of VERU-111 for the treatment of COVID-19. Subjects will receive either 18 mg of VERU-111 or matching placebo orally or through nasogastric tube daily for up to 21 days or until the subject is discharged from the hospital, whichever comes first.
	The primary efficacy endpoint of the study will be the proportion of subjects that are alive without respiratory failure at Day 29. Respiratory failure is defined as endotracheal intubation and mechanical ventilation, extracorporeal membrane oxygenation, high-flow nasal cannula oxygen delivery, noninvasive positive pressure ventilation, clinical diagnosis of respiratory failure with initiation of none of these measures only when clinical decision making is driven solely by resource limitation.
	The total study duration for a subject from screening to follow up visit is planned to be 62 days.
	An evaluation of the effect of VERU-111 on SARS-CoV-2 (COVID-19) compared to the placebo control will be evaluated after the last subject has completed Day 22. This will allow for the decision to move to Phase 3 more quickly if the Phase 2 portion of the study shows a clinically relevant difference in the proportion of subjects that are alive without respiratory failure at Day 22 in the VERU-111 treated groups compared to the Placebo treatment group and VERU-111 is well tolerated in the study.
	Due to the unexpectedly slow recruitment into this study, Veru is conducting an interim analysis after the first 24 subjects have completed Day 15 or have discontinued from the study.
Subjects:	Approximately, 40 subjects are planned to be randomized at a 1:1 ratio into two treatment arms (20 subjects in the VERU-111 treated group and 20 subjects in the Placebo treated group).
	The subjects with documented evidence of COVID-19 infection will be enrolled.
Treatments:	Subjects in the VERU-111 treatment groups will receive standard of care, plus oral daily VERU-111 18 mg for 21 days or until released from hospital.
	Subjects in the Placebo treatment group will receive standard of care, plus a placebo capsule for 21 days or until released from hospital.

Procedures:	Potential study participants will undergo a series of screening evaluations within 2 days prior to randomization. Subjects who give written informed consent and satisfy the selection criteria will be enrolled into the study. The temperature and SpO ₂ levels will be taken every 12 hours starting at baseline.
	Safety evaluations including assessment of adverse events (Days 1-21, Day 29, Day 45, and Day 60), 12-lead electrocardiogram (single) (baseline, Day 15, Day 22, and Day 29) and clinical laboratory results: urinalysis (baseline, Day 22, and Day 29), hematology (baseline, Day 3, Day 9, Day 15, Day 22, and Day 29), and serum chemistry (baseline, Day 3, Day 9, Day 15, Day 22 and Day 29).

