7.0 STUDY MEDICATION

7.1 Enrollment and Blinding

The study will be a randomized, double-blind, placebo-controlled study. The study will be unblinded when the last patient has completed the Day 29 assessments.

An emergency code break will be available to the investigator / pharmacist / investigational drug storage manager. This code break option in IWRS may only be disclosed in emergency situations when the identity of the trial drug must be known to the investigator in order to provide appropriate medical treatment or if required to assure safety of trial participants. If the code break for a patient is opened, the sponsor and CRO will be informed immediately via IWRS notification. The reason for the IWRS unblinding of the subject must be documented on the appropriate eCRF page along with the date and the initials of the person who broke the code.

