9.3.1 Primary Endpoint

The primary endpoint for the study will be the proportion of subjects that are alive without respiratory failure at Day 29. Respiratory failure is defined endotracheal intubation and mechanical ventilation, extracorporeal membrane oxygenation, high-flow nasal cannula oxygen delivery, noninvasive positive pressure ventilation, clinical diagnosis of respiratory failure with initiation of none of these measures only when clinical decision making is driven solely by resource limitation.

This analysis will compare the percentage of subjects that are alive without respiratory failure on Day 22 (responder). The percentage of subjects that meet these criteria in each of the two treatment groups will be summarized and compared observationally and statistically.

The number and percentage of responders will be summarized by treatment group. Responders will be analyzed using a logistic regression model. This model will include treatment as a factor and study site and WHO Ordinal Scale for Clinical Improvement at baseline as a covariates. Odds ratios, standard errors, 95% confidence intervals and p-values for the treatment difference will be presented.

The primary analysis will be performed on the ITT population. Subjects for whom respiratory failure and/or vital status at Day 29 cannot be established will be excluded from the analysis, noting that the number of such subjects is expected to be minimal. A sensitivity analysis will be performed treating these subjects as non-responders. A further sensitivity analysis also be performed on the mITT population.

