#### 7 INTERIM ANALYSIS

Interim analysis was planned in the protocol but will not be performed.

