# STATISTICAL ANALYSIS PLAN. PHASE 2-3-4

Table Number	Table Title	Included in Preliminary Analysis	Included in DSMB (Table No.)	Validation Method	Shell Number (if repeat)
14.1.5.3	Standard of Care (ITT Population)			IP	
14.2	Efficacy Data				
14.2.1	Primary Efficacy Endpoint				
14.2.1.1	Proportion of Subjects Alive and Free of Respiratory Failure by Visit (ITT Population)	Yes		IP	
14.2.1.2	Logistic Regression for Proportion of Subjects Alive and Free of Respiratory Failure by Visit (ITT Population)	Yes		Stat IP	
14.2.1.2a	Responder Rates for Proportion of Subjects Alive and Free of Respiratory Failure by Visit (ITT Population)			Stat IP	
14.2.1.3	Proportion of Subjects Alive and Free of Respiratory Failure by Visit (EE Population)			IP	14.2.1.1
14.2.1.4	Logistic Regression for Proportion of Subjects Alive and Free of Respiratory Failure by Visit (EE Population)			Stat IP	14.2.1.2
14.2.2- 14.2.11	Secondary Efficacy Endpoints				
14.2.2.1	Descriptive Statistics for WHO Ordinal Scale for Clinical Improvement by Visit - With LOCF values (ITT Population)	Yes		IP	
14.2.2.2	Mixed Model for Repeated Measures (MMRM) for Change from Baseline in WHO Ordinal Scale for Clinical Improvement - With LOCF values (ITT Population)	Yes		Stat IP	
14.2.2.3	Descriptive Statistics for WHO Ordinal Scale for Clinical Improvement by Visit - Without LOCF values (ITT Population)			IP	14.2.2.1
14.2.2.4	Mixed Model for Repeated Measures (MMRM) for Change from Baseline in WHO Ordinal Scale for Clinical Improvement - Without LOCF values (ITT Population)			Stat IP	14.2.2.2
14.2.2.5	Descriptive Statistics for WHO Ordinal Scale for Clinical Improvement by Visit - With LOCF values - Screening as Baseline (ITT Population)	Yes		IP	14.2.2.1
14.2.2.6	Mixed Model for Repeated Measures (MMRM) for Change from Baseline in WHO Ordinal Scale for Clinical Improvement - With LOCF values - Screening as Baseline (ITT Population)	Yes		Stat IP	14.2.2.2
14.2.2.7	Descriptive Statistics for WHO Ordinal Scale for Clinical Improvement by Visit - Without LOCF values - Screening as Baseline (ITT Population)			IP	14.2.2.1
14.2.2.8	Mixed Model for Repeated Measures (MMRM) for Change from Baseline in WHO Ordinal Scale for Clinical Improvement - Without LOCF values - Screening as Baseline (ITT Population)			Stat IP	14.2.2.2
14.2.2.9	Area Under Curve of WHO Ordinal Scale for Clinical Improvement (ITT Population)			IP	

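### The protocol schedules a between-arm comparison at the last Day 22 visit but no unblinding before the last Day 29 visit, and Section 9.3.1 pairs a Day 29 primary endpoint with a Day 22 responder; the SAP settles only the responder day

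*Protocol*

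**What the plan says.** **Protocol, Section 2.0 (Design).** The effect of VERU-111 against placebo will be "evaluated after the last subject has completed Day 22". The reason given is speed: "This will allow for the decision to move to Phase 3 more quickly". The criterion is a clinically relevant "difference in the proportion of subjects that are alive without respiratory failure at Day 22", together with good tolerability. The text does not use the word unblinded and does not say who performs the comparison or sees its result.

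**Protocol, Section 7.1.** The study is double-blind. "The study will be unblinded when the last patient has completed the Day 29 assessments." The only exception there is the emergency code break for an individual patient. Section 9.7.1 separately gives the safety board unblinded safety data.

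**Protocol, Section 9.3.1.** The endpoint is stated at Day 29. The analysis sentence that follows counts subjects "alive without respiratory failure on Day 22 (responder". The rule for subjects whose status cannot be established, in the same section, refers to Day 29.

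**SAP.** Section 6.12.1 defines the primary responder at Day 29. Section 6.12.2.6 repeats the analysis at Days 15 and 22 as a secondary endpoint, and Section 6.12.4 treats secondary endpoints as descriptive. Section 7 says: "Interim analysis was planned in the protocol but will not be performed." Section 9, the list of departures from the protocol, covers the added covariates, one dropped secondary endpoint, the cancelled interim, the ITT definition and the new EE population. It mentions neither the Day 22 comparison nor the responder day. The output list in Section 11 has a column headed "Included in Preliminary Analysis", marked for the primary logistic regression and several other efficacy tables. The SAP does not say when that analysis is run or on which data.

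**The concern.** A comparison with placebo needs the treatment codes. The decision it is meant to inform, whether to start Phase 3, belongs to the sponsor, and no independent group is named to keep the result from the sponsor or the sites. Following the summary therefore breaks Section 7.1, and following Section 7.1 means the summary's comparison cannot take place when stated.

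What is at stake is the protection of the last part of the primary data. The last subjects' Day 29 assessments could be made by people aware of the arm results. So could late analysis decisions: SAP Section 6.1.5 leaves EE exclusions to a form signed before database lock, and the SAP amendment table shows the EE definition itself being revised in version 3.0 during the evaluability review.

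The responder wording is a separate fault in the same area. Someone working from the protocol's analysis sentence alone would program the wrong day for the primary endpoint.

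**Working it through.** The documents give no power, event count or derived sample size to reproduce, so the check is one of text and timing.

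**1. Can the summary and Section 7.1 both be followed?** The summary's trigger is the last subject completing Day 22. Section 7.1's trigger is the last patient completing Day 29. The visit windows are ±3 days for each (Protocol 8.6 and 8.7). For the last subject:

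- nominal gap = 29 − 22 = 7 days
- shortest gap = (29 − 3) − (22 + 3) = 26 − 25 = 1 day
- longest gap = (29 + 3) − (22 − 3) = 32 − 19 = 13 days

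The gap is always positive, so a comparison run when the summary says always precedes permitted unblinding.

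**2. How many Day 29 outcomes would be open?** Roughly, weekly enrolment × 7/7 at the nominal gap. The documents do not give the actual late enrolment rate.

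- Protocol 9.7.1 expected recruitment within 4 weeks: 40/4 = 10 per week, so about 10 of 40 open.
- The summary and Section 9.5 say recruitment was unexpectedly slow. At an assumed 1 to 4 per week, about 1 to 4 subjects are open.

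The second range is an assumption. A subject who has already died has a known outcome and would not count.

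**3. Which day is the primary responder?**

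| Place | Day |
|---|---|
| Protocol 2.0, 4.1 and 5.3.1, endpoint | 29 |
| Protocol 9.3.1, endpoint | 29 |
| Protocol 9.3.1, analysed responder | 22 |
| Protocol 9.3.1, missing-data rule | 29 |
| SAP 6.12.1, responder | 29 |

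Only the analysis sentence in 9.3.1 differs. Protocol 9.3 leaves the detailed analysis to the SAP, so Day 29 is the operative day, but the change is not recorded in SAP Section 9.

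**4. Does cancelling the interim analysis also cancel the Day 22 comparison?**

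| | Interim (Protocol 2.0 and 9.5) | Day 22 comparison (Protocol 2.0) |
|---|---|---|
| Trigger | 24 subjects treated for 15 days or discontinued | last subject completes Day 22 |
| Main measure | alive without respiratory failure, Day 15 | same measure, Day 22 |
| Stated reason | slow recruitment | earlier Phase 3 decision |

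These are two separate looks, and the summary describes them in separate paragraphs. SAP Section 7 refers to the one the protocol calls an interim analysis. Nothing in the SAP withdraws the other.

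**The case against.** The strongest defence is that the SAP has already put things right. The primary day is stated as Day 29 almost everywhere, the SAP makes Day 29 the responder day and Day 22 a descriptive secondary, and a reader following the SAP would not analyse the wrong day. That disposes of most of the harm from the 9.3.1 wording. It does not remove the Day 22 comparison from the summary, and SAP Section 9 is silent on both.

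Several stronger readings are tempting and should not be adopted:

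- **Two chances to claim success.** A reader might infer an inflated error rate from testing at Day 22 and again at Day 29. Neither document states a rule that success on either day suffices. The summary ties the Phase 3 decision to a clinically relevant difference and tolerability, not to a significance test.
- **A damaged confirmatory test.** Both documents describe an unpowered proof-of-concept study (Protocol 9.1, SAP 4), so that label does not fit.
- **The preliminary-analysis column as a hidden early look.** The marked tables include days on ventilation and days in ICU, both counted to Day 29 (SAP 6.12.2.4 and 6.12.2.9), and an MMRM reporting visits to Day 60 (SAP 6.12.2.1). These cannot be completed from a Day 22 cut, so the column fits a topline after Day 29 better. The defect is that its timing is undefined.
- **Exposure of Day 60 safety follow-up.** Most of that follow-up would also be open under Section 7.1's own Day 29 unblinding.
- **That the sponsor did see early results.** Nothing shows this. The early use of codes and the sponsor as recipient are inferences from what the comparison requires and what it is for.

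It is also fair to say that dosing ends by Day 21 and that the open outcome is largely death or level of respiratory support, which leaves less room for biased assessment than a subjective scale would.

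**Conclusion.** The inconsistency is real and sits in current text. The protocol's summary and Section 7.1 cannot both be followed, and Section 9.3.1 disagrees with itself on the responder day. The SAP resolves the responder day without recording it as a change and leaves the Day 22 comparison standing.

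The exposure, if the summary is followed, is the last subjects' Day 29 outcomes plus any evaluability decisions still open. The interval is nominally 7 days, or 1 to 13 within the windows. The number of subjects rests on an enrolment rate the documents do not give. The conclusion is conditional on the summary prevailing over Section 7.1, and the effect on the study's inference is limited. It is still worth correcting, because a Phase 3 decision hangs on the comparison and the correction is cheap.

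**What to change.** 1. In Protocol 9.3.1, change the responder day from 22 to 29.
2. Reconcile the summary with Section 7.1. Either withdraw the Day 22 comparison, or state that it is run only after the Day 29 data are locked. If the sponsor wants to keep the earlier timing, name an independent group that performs and sees it, keep the sponsor and sites blinded to Day 29, and amend Section 7.1 to match.
3. List both changes in SAP Section 9.
4. State in the SAP that the tables marked for preliminary analysis are run after the Day 29 lock, and say what that run does with the Day 45 and Day 60 estimates in the marked MMRM.

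The cost is a protocol clarification and a few SAP sentences. Under the first two options the Phase 3 decision moves later by nominally 7 days (1 to 13 within the windows) plus the time to lock. Keeping the look with an independent group avoids that delay but requires setting up the group and its access controls.

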3.0 INTRODUCTION

3.1 Background

Over the last 20 years, a number of viral epidemics have posed a serious global public health risk including Severe Acute Respiratory Syndrome coronavirus (SARS-CoV) in 2002-2003, H1N1 Influenza in 2009, and the Middle East Respiratory Syndrome coronavirus (MERS-CoV) in 2012. Around December 2019, a new viral acute severe respiratory illness emerged. In February 2020, the World Health Organization (WHO) announced that this illness is caused by a coronavirus termed COVID-19. As it was related to SARS-CoV, it was eventually named by the International Committee on Taxonomy of Viruses (ICTV) as SARS-CoV-2 (Cascella 2020). The disease resulting from SARS-CoV-2 infection is called, Coronavirus Disease 2019 (COVID-19). Infection with SARS-CoV-2 and the resulting COVID-19 disease has been declared a global pandemic with over 2,107,450 cases and 136,992 deaths worldwide as of 18 April 2020 and counting (April 18, 2020; Worldometers.info).

SARS-CoV-2 is an enveloped, nonsegmented, positive-sense, single stranded RNA virus with an unusually large RNA genome, a nucleocapsid, and club-like spikes (S protein) that project from their surface and from which they are named. It belongs to the *betacoronavirus* category which includes SARS-CoV and MERS-CoV. These viruses have been responsible for epidemics with variable severity with both respiratory and extra-respiratory clinical manifestations, highly contagious, and mortality rates between 10-35% (Cascella 2020). The coronavirus superfamily (*Coronaviridae*) includes several human pathogens with large RNA genomes, e.g., influenza and viral encephalitis and they are classified into alpha, beta, delta and gamma coronavirus families and then further divided into Lineages A, B, C and D. SARS-CoV-2 is a Lineage B *betacoronavirus* (Gorbalenya 2020).

Viruses have efficient mechanisms that take control of their host's cellular machinery to carry out viral replication, assembly and to exit from the cell to spread infectious virions. Given the spatial distances between the point of virion entry at the plasma membrane to the location in the cell where RNA replication (nucleus) and viral assembly occur in the ER and Golgi and then the newly generated virions have to travel back out to the plasma membrane to egress out of the cell, it is no wonder that the virus's most critical task is to hijack the host's internal transportation system, the cytoskeleton (Ward 2011). The cytoskeleton has three major types of protein filaments: microfilaments (actin), microtubules (tubulin), and intermediate filaments. The principal ones involved in viral replication and trafficking (transport) are microtubules and actin since these are the two main filament systems involved in cellular transport (Ward 2011).

Microtubules are important for cell shape, transport, motility, and cell division (Heald 2002). Microtubules are dynamic long polar fibers/filaments that result from the polymerization of α and β tubulin heterodimer subunits with a positive end located at the plasma membrane and a minus end facing the nucleus at the microtubule organizing center (MTOC). From the MTOC, microtubule fibers radiate out from the nuclear area towards the periphery of the cell. Microtubules are dynamic network systems, meaning that, they undergo rapid polymerization

(add α and β tubulin subunits heterodimers) to grow, and subsequent rapid depolymerization (remove α and β tubulin subunits heterodimers) to shrink. This "dynamic" growing and shrinking serves the constantly changing transportation requirements of the cell. Large macromolecules, like viruses, engage with specialized motor proteins (kinesins and dyneins) (Dohner 2005; Biswas 2014; Han 2012; Hara 2009). Kinesins and dyneins attach, carry, and move the virus cargo up and down these microtubule tracks to travel long distances to reach the different compartments within the cell (Ward 2011; Simpson 2020; Cooper 2000).

Microtubule based transportation is a critical aspect of viral replication (Naghavi 2017; Dohner 2005). In fact, viral infection or expression of viral proteins alters the organization of the microtubular networks to serve their need to replicate and spread infectious virion. Microtubules not only facilitate infection, but microtubules are actively manipulated by viruses (Naghavi 2017). Furthermore, microtubule inhibiting agents that disrupt microtubule networks suppress viral infection (Rudiger 2016).

Virus-cell surface interactions, virus entry and internalization-

Although microtubules are located within the cell, they are able to influence the viral infection from the onset. Viruses utilize specific sites and proteins to attached to the cell surface. The spatial organization of these surface receptors and entry factors are controlled in part by the polarization of the microtubular array (Naghavi 2017). When added early, nocodazole, a microtubule depolymerizing drug, decreased mouse hepatitis coronavirus virus infection by affecting plasma membrane entry by endocytosis (Burkard 2014). There are apparently other ways that entry and internalization may occur as human coronavirus NL63 internalization and vesicle entry was not affected by nocodazole (Milewska 2018).

In the case of SARS-CoV, the first stage of interaction with the microtubule cytoskeleton occurs when the Spike (S) protein mediated attachment to the cell surface (Ren 2015). After binding, the virus particles actively rearrange the cytoskeleton by regulating the FAK/Cofilin/Rac/Cdc42 pathway (Lv 2019).

Virus intracellular transport via microtubules to the perinuclear region-

Many viruses require microtubules at cell entry for efficient nuclear targeting (Dohner 2005). Vesicular transport occurs via microtubule trafficking and the corresponding specialized motor proteins. In the case of the Mouse Hepatitis Coronavirus Virus, the early secretory pathway is important in the formation of the replication complex (Knoops 2010; Oostra 2007). Intracellular transport of the endocytosed vesicles containing coronavirus utilizes S-protein bound to β - tubulin on microtubules to locate to the perinuclear region of the cell. Viruses can also modulate microtubular dynamics to promote rapid transport to nucleus (Naghavi 2017; Suomalainen 2001). Coronaviruses may also have interactions of S proteins with the specialized motor proteins like kinesins and dyneins (Rudiger 2016).

Virion replication and assembly and egress of infectious viral particles out of the cell-

Virus particle assembly occurs in the ER-Golgi intermediate compartment (ERGIC) and is orchestrated by the M protein. M provides the scaffold for virion morphogenesis and M-S and M-N interactions facilitate the recruitment of structural components to the assembly site.

Coronavirus particles budding into the ERGIC are transported in smooth walled vesicles and trafficked via microtubules for release by exocytosis. Host factors, specifically, the interactions between the cytoskeleton and other structural proteins are essential in this process. Interactions between tubulin and the cytosolic domain of the S protein of human coronavirus-229E, human coronavirus-NL63, and TGEV are required for successful assembly and release of viral particles (Reviewed in Fung 2019). RNA viruses utilize diverse structures within the cytoskeleton for their replication which rely on microtubules to form and function (Naghavi 2017). Nocodazole, a microtubule depolymerizing agent, blocks the movement and fusion of capsids and nucleoprotein particles to the budding ER/Golgi compartments to form virions as well as the secretory microtubule trafficking to egress new virions resulting in reduced virus yields (Eichwald 2012; Criglar 2014; Dohner 2005).

To evaluate early assembly events, alpha (HCoV-229E, HCoV-NL63, and TGEV) and beta (SARS-CoV) coronaviruses S proteins were treated with nocodazole. The pharmacological action of nocodazole is the inhibition of tubulin polymerization. Untreated cells had long and filamentous tubulin structures (microtubules) and the S protein accumulated near the nucleus (ERGIC) and less S protein distributed in the cytosol, whereas the nocodazole treated cells had dispersed and patchy tubulin fragments and the S proteins were "differentially distributed", or scattered throughout the cytoplasm (Rudiger 2016). Also, following nocodazole treatment, M protein amount was decreased and there was a reduced colocalization of S and M proteins (Rudiger 2016). Nocodazole treatment resulted in both a significant reduction in viral particles and these particles had very little S protein, and thus, the virions were less infectious as well (Rudiger 2016). In fact, nocodazole treatment at all time points resulted in significantly lower virus titers in cell culture supernatant versus untreated infected cells (Rudiger 2016).

In summary, tubulin interacts with the cytoplasmic domain of *alphacoronavirus* and *betacoronavirus* SARS-CoV spike S proteins. Rudiger et al. (2016) conclude that the reduction in infectious virus titer following treatment with a drug that causes microtubule depolymerization is mainly because there is less S protein present at the assembly site due to impaired S protein-microtubule transport and that the incorporation process of S protein itself into virions is tubulin-dependent. Furthermore, disruption of microtubule trafficking impaired the egress of these poorly assembled virions with less surface spike S proteins, less infectious, out of the cell. A microtubule depolymerizing agent may be effective in treating in treating coronavirus infection to disrupt microtubule trafficking critical for virus replication cycle.

Colchicine-like Activity

The central mechanism of colchicine clinical anti-inflammatory and anti-viral activities is based on its ability to bind the "colchicine binding" sites on alpha and beta tubulin which when incorporated into microtubule block subsequent microtubule polymerization (Slobodnick 2018). Inhibition of tubulin polymerization is responsible for the effects of colchicine on cell migration, cytokine release, and intracellular trafficking (antiviral) and disruption of inflammatory cell activities seen for acute gout and familial Mediterranean fever. Colchicine modulates leucocyte mediated inflammatory activities including inhibition of leucocyte production of superoxides and release of various cytokines and pyrogens (Slobodnick 2018). Colchicine-like agents may be useful to treat the "cytokine storm" seen with SARS-CoV 2. IL-18 is a member of the IL-1 cytokine family and unopposed elevated levels of IL-18 concentrations have been associated with macrophage activation syndrome and poor clinical outcomes in severe inflammatory and septic shock conditions (Verweyen 2020). Interestingly, colchicine abrogates IL-1 β and IL-18 overexpression by reducing its transcription to reduce severe inflammation and septic shock. Verweyen et al. (2020) also showed that colchicine as well as nocodazole abrogated IL18 expression confirming that microtubule depolymerization is the mechanism.

